## 5.2 Handling of Missing Data

The CMAI is utilized as the primary efficacy assessment of a subject’s level of agitated behaviors. The CMAI consists of 29 items all rated on a 1 to 7 scale with 1 being the “best” rating and 7 being the “worst” rating. The CMAI Total Score is the sum of ratings for all 29 items. The possible total scores are from 29 to 203. The CMAI Total Score will be unevaluable if less than 24 of the 29 items are recorded. If 24 to 28 of the 29 items are recorded, the total score will be the mean of the recorded items multiplied by 29 and then rounded to the first decimal place.

CCI  
[Redacted text block]

The primary efficacy variable is the change from baseline to Week 12 in the CMAI total score.

In general, missing data will be handled by analysis of Mixed effect Model Repeat Measurement (MMRM) methodology based on observed-case (OC) data from protocol-specified visits in the ITT population under the assumption of missing at random (MAR).

The OC dataset consists of actual observations recorded at each visit during the double-blind acute treatment phase, and no missing data will be imputed.

CCI  
[Redacted text block]

## **6 Study Conduct**

### **6.1 Subject Disposition and Reasons for Discontinuations**

Subject disposition is summarized for the randomized sample. Disposition is summarized by treatment group and by subgroup of gender, age (<65; >=65 and <75; or >=75), race, and region (North America or Other).

Reasons for discontinuation will be summarized for the randomized sample by treatment group and by subgroup of gender, age, race, and region.

### **6.2 Treatment Compliance**

Based on the Study Medication panel of the CRF, compliance in taking study medication is calculated by dividing the number of tablets taken by the total number of tablets the subjects were scheduled to take during the study period. For lost-to-follow up subjects, last study medication end date record will be used as the treatment end date.

### **6.3 Protocol Deviation**

Protocol deviations are summarized by center and type of deviation for randomized subjects by treatment group. A listing of protocol deviations will also be generated.

## **7 Baseline Characteristics**

### **7.1 Baseline Definition**

For analyses of the double blind treatment period data, the baseline is the Baseline measurement (expected to be at Day 0). Baseline measurement is defined as the last available measurement prior to the start of double-blind study medication.

## 7.2 Demographic Characteristics

Baseline demographic characteristics including age, gender, race, ethnicity, height, weight, waist circumference, and body mass index (BMI) will be tabulated by treatment group for all randomized subjects. Additional summaries by the following subgroups will be also generated: by gender, by age group (<65; >=65 and <75; or >=75), by race, and by region (North America or Other).

Mean, range and standard deviation will be used to describe continuous variables such as age. Frequency distributions will be tabulated for categorical variables such as race.

## 7.3 Disease History

A summary of medical, psychiatric, neurological (excluding Alzheimer's), and Alzheimer's disease history will be presented for the Randomized Sample (by treatment group and overall).

## 7.4 Baseline Disease Characteristics

For the Randomized Sample, baseline and baseline disease characteristics will be summarized by treatment group and overall. The following baseline characteristics will be summarized at baseline: number (%) of institutionalized / non institutionalized subjects; CMAI total score; CCI [REDACTED]  
[REDACTED] CGI-S score, NPI total score; NPI-AA item score; MMSE score; CCI [REDACTED] CCI [REDACTED]  
[REDACTED]

Number of subjects with presence of psychotic symptoms will be summarized at baseline using NPI Delusion and Hallucination score. The counts will be provided for the following categories: NPI item score >=4, >=5, >=6 on either hallucination or delusion score.

All patients randomized under the original protocol and amendment 1 are assumed to be institutionalized and will be included in the institutionalized subgroup.

## **8 Efficacy Analysis**

All efficacy analyses pertaining to the double blind treatment period will be performed on the Efficacy Sample, and subjects will be included in the treatment group as randomized. Statistical comparisons are based on 2-sided, 0.05 significance levels.

NPI endpoints are collected using NPI-NH for institutionalized subjects and NPI/NPI-NH for non-institutionalized subjects. Since each score derivation of the NPI items is based on the frequency and severity scores only, no distinction will be made due to the instrument used. All analysis of NPI based endpoints will be based on totality of data, unless specified otherwise.

### **8.1 Primary Efficacy Endpoint**

The primary efficacy endpoint is the change from the baseline (Day 0 visit) to the end of the double blind treatment period (Week 12 visit) in CMAI Total Score.

#### **8.1.1 Primary Efficacy Analysis**

The primary endpoint will be analyzed using a mixed-effect model repeated measure (MMRM) model. The primary efficacy outcome measure is the mean change from baseline (Day 0 visit) to the end of the double-blind treatment period (Week 12 visit) in the CMAI total score. The primary statistical comparison of interest is brexpiprazole flexible dose versus placebo. The null hypothesis is that there is no difference between the brexpiprazole treatment group and placebo in change from baseline to endpoint in CMAI total score. The comparison will be made at the significance level of  $\alpha = 0.05$  (2-sided).

The primary analysis will be performed on the Efficacy Sample which includes all randomized subjects who took at least one dose of IMP in the double blind treatment period and who have both a baseline and at least one post-randomization CMAI Total Score during the double blind treatment period. The primary efficacy analysis will be performed by fitting a MMRM analysis with an unstructured (UN) variance covariance structure in which the change from the baseline in CMAI Total Score (Week 2, 4, 6, 8, 10, 12) will be the dependent variable based on the OC data set. The model will include fixed class-effect terms for treatment (brexpiprazole and placebo), trial center, visit week, and an interaction term of treatment by visit week and include the interaction term of baseline values of CMAI Total Score by visit week as covariates. The primary comparison between a brexpiprazole and the placebo arm at Week 12 will be estimated as

the difference between Least Squares (LS) means from the interaction term of treatment by visit week utilizing the computing software SAS procedure PROC MIXED.

CCI [Redacted]

[Redacted]

[Redacted]

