## 3.6. Measures to Minimize/Avoid Bias

### 3.6.1. Randomization

During the trial, administration of the IMP will be double-blind. In other words, neither the investigator nor the subject will have knowledge of the treatment assignment (ie, placebo or brexpiprazole). Treatment assignments will be based on a computer-generated randomization code provided by the Otsuka Pharmaceutical

Protocol 331-12-284

Development & Commercialization, Inc (OPDC) Biometrics Department. Sponsor personnel, including those involved in monitoring, data management, and data analysis, will not have access to the treatment code during the trial. Access to the treatment codes will be restricted to personnel charged with generating and maintaining randomization files, packaging trial medication, operating the IVRS/IWRS, and reporting SAEs to regulatory agencies. The randomization will be stratified by center. Subjects will be randomized to brexpiprazole or placebo in a 1:1 ratio within each stratum.

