### 3.7.2. Efficacy Assessments

It is required that adequately trained and experienced clinicians administer the CMAI, NPI-NH, NPI/NPI-NH, CGI-S, CCI, CCI. In addition, the raters must be certified for this trial to administer the CMAI, NPI-NH, and NPI/NPI-NH. Notations in the subject's trial records should substantiate the ratings. Training, certification, and materials for rating will be provided by a rater training group.

A caregiver must be identified during the screening period for participation in the interview for the CMAI, NPI-NH, NPI/NPI-NH, and other applicable trial assessments. In addition to providing responses to trial questionnaires, the identified caregiver will be interviewed by the trial personnel regarding the subject's general medical condition, behavioral symptoms, and activities of daily living. If the subject is in an institutionalized setting, the identified caregiver will gather information from several informants, including staff from the day, afternoon, and night shifts, as well as from reliable family members or friends, in order to provide an accurate and comprehensive overview of the subject's behavioral symptoms and condition. If the subject is in a non-institutionalized setting, the identified caregiver can gather information from the caretaker (if different than the identified caregiver) or from other informants who are in a

Protocol 331-12-284

position to observe the subject and provide information regarding behavioral symptoms and activities of daily living. Details on the caregiver requirements can be found in [Section 3.3.1](#).

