#### **4 Sample Size and Power Justification**

The sample size was calculated based on the treatment effect of 6.5 points with a standard deviation (SD) of 16.5 in the change from baseline (Day 0 visit) to the end of the double-blind treatment period (Week 12 visit) in the CMAI total score, to achieve 85% power at a 2-sided alpha level of 0.05. The resulting sample size is 117 subjects/arm. After allowance of 10% non-evaluable subjects, it results in a sample size of 130 subjects/arm, which means the total sample size is 260 subjects. The sample size was estimated based on 1:1 randomization ratio (brexpiprazole:placebo). The randomization will be stratified by center.

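### The primary MMRM does not adjust for baseline care setting and so forgoes a modest gain in precision and in protection against chance imbalance

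*SAP*

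**What the plan says.** **Model.** SAP 8.1.1 states: "The model will include fixed class-effect terms for treatment (brexpiprazole and placebo), trial center, visit week". It adds treatment-by-visit and baseline CMAI-by-visit interactions, with an unstructured covariance matrix over Weeks 2, 4, 6, 8, 10 and 12. Protocol 7.4.1 and the synopsis name the same fixed effects, again without setting. SAP 8.2 uses the same method for the CGI-S.

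**Randomization.** Protocol 3.6.1: "The randomization will be stratified by center". No other stratum is named.

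**Setting as a baseline factor.** SAP 7.4 tabulates it by arm and has a rule for early enrollees: "All patients randomized under the original protocol and amendment 1 are assumed to be institutionalized". Under Protocol 3.3 and 3.8.3, a subject who moves between settings is withdrawn, so the factor does not change on treatment.

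**CMAI information.** Protocol 3.7.2 says that for an institutionalized subject "the identified caregiver will gather information from several informants, including staff from the day, afternoon, and night shifts". For a non-institutionalized subject, the caregiver has the option of consulting the caretaker or others.

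**Sample size (SAP 4).** The inputs are given as follows: "The sample size was calculated based on the treatment effect of 6.5 points with a standard deviation (SD) of 16.5". With a power target of 85% and two-sided alpha of 0.05, the plan arrives at 117 evaluable subjects in each arm, and a 10% allowance raises this to 130 randomized per arm.

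**The concern.** Setting could plausibly relate to change in CMAI. It affects who contributes information and how closely the subject is supervised. It also follows enrolment era, because non-institutionalized subjects were admitted only from Amendment 2. If mean change differs by setting within centers and at equal baseline score, that variation stays in the error term. A chance difference between arms in the share institutionalized would then move the treatment estimate. Adjusting for a factor already collected would remove both effects.

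Two features of the stated model leave room for this despite the center term. First, center enters as a main effect only, so it absorbs a setting difference that is constant over visits but not one that develops by Week 12, where the primary contrast is taken. Second, a center may hold both settings. Protocol 3.3 plans about 260 randomized subjects at about 65 sites (260/65 = 4 per site), and SAP 10.2 provides for pooling small centers under a redacted rule. A pooled center can mix settings even when each site has only one.

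**Working it through.** **Inputs from SAP 4:** effect 6.5, SD 16.5, two-sided alpha 0.05, power 85%, 117 evaluable and 130 randomized per arm.

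**Assumptions, not in the documents:** share institutionalized p = 0.1 to 0.5; difference D in mean CMAI change between settings, at the same center and baseline score, of 5 to 10 points.

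**1. Reproduce the plan.** 2 × (1.960 + 1.036)² × 16.5²/6.5² = 115.7, so 116 per arm by the normal approximation. The two-sample t calculation gives 116.7, so 117. Then 117/0.9 = 130 per arm, 260 in total. The stated figures reproduce. Power at 117 per arm is 85.4% (normal) or 85.1% (t).

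**2. Ceiling on the gain, with no help from center.**
- Variance share = p(1−p)D²/16.5².
- Power is recomputed with residual variance 16.5² − p(1−p)D².
- SD of the between-arm difference in share = √(2p(1−p)/117), which is 0.039 at p = 0.1 and 0.065 at p = 0.5.
- 95% limit of the shift = 1.96 × that SD × D.

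| p | D | variance share | power with term (from 85.4%) | 95% limit of shift |
|---|---|---|---|---|
| 0.1 | 5 | 0.8% | 85.7% | ±0.38 |
| 0.1 | 10 | 3.3% | 86.5% | ±0.77 |
| 0.5 | 5 | 2.3% | 86.2% | ±0.64 |
| 0.5 | 10 | 9.2% | 88.5% | ±1.28 |

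Precision and imbalance protection are one quantity seen two ways. The planned standard error is 16.5 × √(2/117) = 2.16. At p = 0.5 and D = 5 the SD of the shift is 0.065 × 5 = 0.33, and 0.33²/2.16² = 2.3%, the same variance share. The chance shift is therefore already inside the standard error, which is why type I error is not inflated.

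**3. Allow for center.** Simulation: 60 centers of 4 subjects, allocated 2:2 within center, p = 0.5, one outcome per subject, center-adjusted analysis with and without a setting term, 3,000 replicates.

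| centers open to both settings | D | imbalance SD | power without term | power with term |
|---|---|---|---|---|
| none | 5 | 0 | 87.4% | 87.4% |
| none | 10 | 0 | 89.7% | 89.7% |
| 30% | 5 | 0.035 | 87.7% | 87.6% |
| 30% | 10 | 0.035 | 87.9% | 88.6% |
| all | 5 | 0.065 | 85.8% | 86.3% |
| all | 10 | 0.064 | 86.7% | 88.9% |

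Each power figure has a Monte Carlo standard error of about √(0.87 × 0.13/3000) = 0.6 points. Mean estimates ran from −6.465 to −6.556 against a true −6.5, with or without the term, so omission does not bias. With 30% of centers mixed, the 95% limit of the shift is 1.96 × 0.035 × 5 = 0.34 or, at D = 10, 0.69 points.

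**Limits of the simulation.** It has one time point, so it does not test the missing center-by-visit term. It also assumes complete 2:2 allocation in every center and no pooling.

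**4. Cost.** Setting uses 1 degree of freedom and setting-by-visit uses 6 − 1 = 5, so six in total, against 2 × 117 = 234 evaluable subjects.

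**The case against.** The strongest reply is that the model already handles most of this. Center is both a stratum and a fixed effect, allocation is in fixed blocks (Protocol 3.2), and baseline CMAI-by-visit is in the model. If every center enrols one setting, the simulated imbalance is zero and the term gains nothing. This stands, and it is why the gain is modest.

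The mechanism is also thin. Both settings use the same 29-item scale, certified raters, one identified caregiver and the same recommended minimum contact, and other informants are provided for in both. A stable informant effect on level enters the baseline score and largely cancels in change. Nothing in the documents shows that CMAI change differs by setting. This stands too: D is an assumption throughout.

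Redaction limits the point. Text after the model statement in SAP 8.1.1, all of 8.1.2 and 8.1.3, and part of 8.1.4 are blacked out, and SAP 7.4 refers to an institutionalized subgroup. A supportive or subgroup analysis by setting may exist. It would not put setting into the stated primary model.

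A reader might infer that precision and control of chance imbalance are lost, or that the primary result would be biased. The documents do not support either reading. Center stratification and the center effect retain much of that control, treatment is randomized independently of setting, and the simulation shows no bias.

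**Conclusion.** The point holds as a modest prespecification improvement, not as the correction of an error. The stated primary model omits a recorded baseline factor that is fixed on treatment and not a stratum. Center only partly stands in for it, because it has no by-visit term and because mixed or pooled centers are possible.

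Under assumed setting differences of 5 to 10 points, the simulated power gain is about 0 to 2 points. The closed-form ceiling, at a 50:50 mix and D = 10 with no absorption by center, is 88.5 − 85.4 = 3.1 points. The 95% limit of the chance shift is at most about 0.6 to 1.3 points of the planned 6.5, for a 50:50 mix with no center balancing. It is smaller when centers are single-setting or the mix is uneven. All these sizes rest on a split and a setting effect that neither document gives.

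**What to change.** Before unblinding, add baseline care setting and setting-by-visit week as fixed effects in SAP 8.1.1. The change carries into the CGI-S analysis in 8.2. Classify subjects enrolled under the original protocol and Amendment 1 by the SAP 7.4 rule. Record the change from the model in Protocol 7.4.1 and the synopsis, so that the two documents do not disagree on the primary analysis. If the redacted text already holds an analysis by setting, align it with these terms.

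The cost is about six degrees of freedom and a documented change in both places. Two drawbacks remain. Amendment 3 states that it broadened the definition of an institutionalized setting (the SAP 3 examples no longer appear in Protocol 3.1), so the covariate may not mean quite the same thing across enrolment eras. And there is little to gain where centers are single-setting.

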8.1.2 CCI [Redacted]

[Redacted]

CCI [Redacted]

[Redacted]

[Redacted]

8.1.3 CCI [Redacted]

[Redacted]

[Redacted]

[Redacted]

CCI [Redacted]

[Redacted]

[Redacted]

[Redacted]

[Redacted]

[Redacted]

### 8.1.4 Subgroup Analyses for Primary Efficacy Endpoint

Subgroup analyses of change from baseline in CMAI Total Score to every study week in the double blind treatment period will be performed by the following factors:

- Gender
- Race (White and All Other Races)
- Age group (<65; >=65 and <75; or >=75)
- Region (North America and Other)

CCI [REDACTED]  
[REDACTED]  
[REDACTED]  
[REDACTED]  
[REDACTED]  
[REDACTED]  
[REDACTED]  
[REDACTED]

### 8.2 Key Secondary Analysis

The key secondary efficacy variable is the change from baseline to endpoint in the CGI-S score, as related to agitation. It will be analyzed by the same statistical methodology specified for the analysis of the primary efficacy variable, based on the Efficacy Sample. In order to control the overall type I error rate for this key secondary efficacy analysis, a hierarchical testing procedure will be used so that the overall experiment-wise type I error rate is maintained at 0.05. Thus, if the primary efficacy analysis for the CMAI total score yields a statistically significant result at 0.05 (2-sided) for the comparison of brexpiprazole versus placebo, then the comparison for key secondary efficacy variable (CGI-S score) will be tested at an alpha level of 0.05 (2-sided).

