### **3.5. Outcome Variables**

#### **3.5.1. Primary Efficacy Variable**

The primary efficacy variable is the change from baseline to Week 12/ET in the CMAI total score. The primary analysis will use a mixed-effect model repeated measure (MMRM) approach.

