#### **3.5.2. Key Secondary Efficacy Variable**

The key secondary efficacy variable is the change from baseline to Week 12/ET in the Clinical Global Impression-Severity of Illness (CGI-S) score, as related to agitation.

Protocol 331-12-284

**3.5.3.** CCI [Redacted]

[Redacted]

[Redacted]

[Redacted]

[Redacted]

[Redacted]

[Redacted]

**3.5.4.** CCI [Redacted]

[Redacted]

[Redacted]

[Redacted]

[Redacted]

[Redacted]

[Redacted]

[Redacted]

**3.5.5.** CCI [Redacted]

[Redacted]

[Redacted]

[Redacted]

[Redacted]

[Redacted]

Protocol 331-12-284

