## 7.4. Efficacy Analyses

### 7.4.1. Primary Efficacy Analysis

The primary endpoint will be analyzed using an MMRM model. The primary efficacy outcome measure is the mean change from baseline (Day 0 Visit) to the end of the double-blind treatment period (Week 12 visit) in the CMAI total score. Details of sensitivity analyses under the assumption of MNAR will be provided in the statistical analysis plan (SAP). The null hypothesis for the comparison of brexpiprazole flexible dose versus placebo is that there is no difference between the brexpiprazole treatment group and placebo in change from baseline to endpoint in CMAI total score. The comparison will be made at the significance level of  $\alpha = 0.05$ .

The statistical comparison will be performed by fitting a MMRM analysis with an unstructured variance covariance matrix in which the change from baseline (Day 0 Visit) in CMAI total score (at Weeks 2, 4, 6, 8, 10, and 12) will be the dependent variable based on the OC dataset. The model will include fixed class-effect terms for treatment, trial center, visit week, and an interaction term of treatment by visit week. The model will also include a random effect for subject and the interaction term of baseline (Day 0 visit) by visit week as covariates. The primary comparison between the brexpiprazole and the placebo groups at Week 12 will be estimated as the difference between the least squares (LS) means utilizing the computing software SAS procedure PROC MIXED.

CCI

The primary analysis CCI will be performed on the Efficacy Sample.

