
Section 7.4.1 Primary Efficacy Analysis
	
The primary endpoint will be analyzed using a mixed-effect model repeated measure (MMRM) model. The primary efficacy outcome measure is the mean change from baseline to the endpoint in the CMAI total score. CCI
 
[REDACTED]
 
The null hypothesis for the comparison of brexpiprazole flexible dose versus placebo is that there is no difference between the brexpiprazole treatment group and placebo in change from baseline to endpoint in CMAI total score. The comparison will be made at the significance level of alpha = 0.05.
 
The statistical comparison will be performed by the MMRM analysis with an unstructured variance covariance matrix for the repeated measures in which the change from baseline to endpoint in CMAI total score will be the dependent variable based on the OC dataset. The model will include fixed class-effect terms for treatment, trial center, visit week and an interaction term of treatment by visit week and include the interaction term of baseline by visit week as a covariate.
	
The primary endpoint will be analyzed using a mixed-effect model repeated measure (MMRM) model. The primary efficacy outcome measure is the mean change from baseline (Day 0 Visit) to the <del>endpoint</del> end of the double-blind treatment period (Week 12 visit) in the CMAI total score. CCI
 
[REDACTED]
 
The null hypothesis for the comparison of brexpiprazole flexible dose versus placebo is that there is no difference between the brexpiprazole treatment group and placebo in change from baseline to endpoint in CMAI total score. The comparison will be made at the significance level of alpha = 0.05.
 
The statistical comparison will be performed by <del>the fitting a</del> MMRM analysis with an unstructured variance covariance matrix <del>for the repeated measures</del> in which the change from baseline <del>to endpoint</del> (Day 0 Visit) in CMAI total score (at Weeks 2, 4, 6, 8, 10, and 12) will be the dependent variable based on the OC dataset. The model will include fixed class-effect terms for treatment, trial center, visit week <del>and an interaction term of treatment by visit week and include</del>

Protocol 331-12-284

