**9.7 Mini-Mental State Examination (MMSE)**

The mean changes from baseline to Week 12 (OC) and the last visit in the double blind treatment period in MMSE will be tabulated and analyzed by treatment group using ANCOVA. The ANCOVA model for the OC data set will include the baseline item score as covariate and treatment group as main effect. The ANCOVA model for last visit will include the baseline item score as covariate, and study center, treatment group as main effects. The analyses will be performed for Safety Sample.

**9.8** CCI [REDACTED]

[REDACTED]

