### Study Day and Visit Window

Week	Target Day a	Study Day Interval a
1	7	2-10
2	14	11-17
3	21	18-24
4	28	25-31
5	35	32-38
6	42	39-45
7	49	46-52
8	56	53-59
9	63	60-66
10	70	67-73
11	77	74-80
12	84	81-91 b

a Relative to the first day of IMP in the double blind treatment period.

CCI [REDACTED]

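### Is the time point of the key secondary CGI-S test left open because it is labelled Week 12/ET in some places and endpoint in others?

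*SAP*

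**What the plan says.** The current text states the timing of the key secondary variable four times.

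- SAP 8.2: "The key secondary efficacy variable is the change from baseline to endpoint in the CGI-S score, as related to agitation".
- Protocol 7.4.2 has the same sentence as SAP 8.2.
- Protocol 3.5.2: "The key secondary efficacy variable is the change from baseline to Week 12/ET in the Clinical Global Impression-Severity of Illness (CGI-S) score".
- The protocol synopsis, under Criteria for Evaluation, agrees with 3.5.2.

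SAP 8.2 and Protocol 7.4.2 both then say that CGI-S is analysed by the method laid down for the primary variable. Both test it at 0.05 (2-sided) only after a significant primary result.

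The primary variable carries the same mix of labels. Protocol 3.5.1 says: "The primary efficacy variable is the change from baseline to Week 12/ET in the CMAI total score". The null hypothesis in Protocol 7.4.1, repeated in SAP 8.1.1, is that "there is no difference between the brexpiprazole treatment group and placebo in change from baseline to endpoint in CMAI total score". SAP 8.1 is explicit and defines the primary endpoint as the change from the Day 0 baseline "to the end of the double blind treatment period (Week 12 visit) in CMAI Total Score".

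**The concern.** The labels are not synonyms. A Week 12/ET assessment is also made when a subject withdraws early (Protocol 3.8.3), so it can fall well before Week 12. Read literally, a change to Week 12/ET is close to a change to the last assessment. A change to Week 12 is a modelled mean at one visit. The SAP knows the difference, because for MMSE it lists both: "The mean changes from baseline to Week 12 (OC) and the last visit in the double blind treatment period in MMSE".

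The amendment history adds to the suspicion. Amendment 2 revised the CMAI outcome sentence to name the "end of the double-blind treatment period (Week 12 visit)", and the CGI-S sentence did not get the same edit. A reader could infer that something else was meant for CGI-S.

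The stake would be the one secondary test under error control. If two analyses were both admissible, the choice between them could be made after the data were seen, and the 0.05 level would not hold.

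**Working it through.** **1. The labels side by side** (current text, amendment log left out)

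| Variable | Week 12/ET | Endpoint | Week 12 named |
|---|---|---|---|
| CGI-S | Synopsis (Criteria for Evaluation); Protocol 3.5.2 | Protocol 7.4.2; SAP 8.2 | none |
| CMAI | Synopsis (Criteria for Evaluation); Protocol 3.5.1, 3.7.2.1 | Synopsis (sample size); Protocol 7.1; null hypothesis in Protocol 7.4.1 and SAP 8.1.1 | Synopsis (Statistical Methods); Protocol 7.4.1; SAP 4, 5.2, 8.1, 8.1.1 |

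The split for CGI-S is not protocol against SAP. It lies between the variable definitions and the analysis sections, and the two analysis sections agree. The first two columns also hold CMAI, whose time point is not in doubt, so neither label can by itself signal a different time point.

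**2. Following the cross-reference.** The primary method (Protocol 7.4.1, SAP 8.1.1) is an MMRM with unstructured covariance on observed cases at Weeks 2, 4, 6, 8, 10 and 12. The treatment comparison is the difference in LS means at Week 12, taken from the treatment-by-visit term. Protocol Table 3.7-1 schedules CGI-S at baseline and at the same six visits, so the model carries over without adaptation. SAP 5.2 says observed-case data are not imputed. The model therefore yields contrasts by visit and has no last-assessment contrast to report.

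**3. What endpoint means here.** Protocol 7.1 bases the sample size on the CMAI change to the endpoint. SAP 4 gives the same calculation with the change to the Week 12 visit. The inputs are identical: difference 6.5, SD 16.5, power 85%, 2-sided alpha 0.05.

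- Normal approximation: n = 2 × (1.960 + 1.036)² × 16.5² / 6.5² = 2 × 8.978 × 272.25 / 42.25 = 115.7, so 116 per arm.
- Noncentral t: 117 per arm, power 0.851. This is the stated figure.
- Allowance for 10% non-evaluable: 117 / 0.90 = 130 per arm, 260 in total, as stated.

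It is one calculation in two wordings, so the documents themselves equate endpoint with the Week 12 visit. SAP 8.1.1 does so again, using endpoint in its null hypothesis and Week 12 for the comparison that tests it.

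**4. What Week 12/ET means here.** It is a column heading in Protocol Table 3.7-1 and the title of Protocol 3.7.1.4, that is, the name of a visit at which scales are collected. Protocol 3.5.1 gives CMAI the same label and in its next sentence names MMRM as the analysis.

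**5. Where the SAP does mean the last visit.** SAP 9.5 (body weight) and 9.7 (MMSE) name the last visit beside Week 12 and attach an ANCOVA. SAP 8.2 does neither.

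**6. Visit windows.** SAP 10.1 assigns assessments by study day, counted thus: "Relative to the first day of IMP in the double blind treatment period". Week 12 is Days 81 to 91. On the visible rule, an assessment before Day 81 is not a Week 12 value. The footnote to that window and the text after the convention are blacked out, so nothing more can be said about early-termination visits.

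**7. What two free readings would cost.** This is an illustration only. Suppose the gate is passed, CGI-S has no true effect, and success could be declared on either of two tests at |Z| > 1.960 with correlation ρ. The chance of a false positive is 1 − P(|Z₁| ≤ 1.960 and |Z₂| ≤ 1.960):

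| ρ (assumed) | 0.70 | 0.80 | 0.90 | 0.95 |
|---|---|---|---|---|
| Error | 0.083 | 0.078 | 0.070 | 0.065 |

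With one reading fixed in advance the level is 0.05. Steps 2 to 5 fix one reading.

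**The case for a change.** The best case for a change is that a confirmatory test should carry its time point in its own definition. Here the reader must follow a cross-reference, and two protocol sections use a label that covers early withdrawals. The sponsor tidied the CMAI sentences and could have tidied this one at almost no cost.

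Part of this stands. The labels do differ, endpoint has no visible formal definition, and SAP 8.2 would read better if it named the Week 12 visit.

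The inference to a different analysis does not stand. The edit to the CMAI text is history, and it left endpoint in the CMAI null hypothesis. The word's survival in the CGI-S sentence therefore shows no difference in meaning. The last-assessment reading also needs an efficacy analysis that no visible section specifies. Nor can the documents be faulted for not defining the term or mapping early-termination visits, because much of the relevant text (Protocol 7.3, parts of SAP 5.2 and 10.1) is blacked out.

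**Conclusion.** The concern does not call for a change. The inconsistency is clerical, and the plan's own cross-reference fills the gap. An analyst who follows SAP 8.2 fits the primary MMRM to CGI-S and tests the Week 12 contrast at 0.05, and the visible text offers no other efficacy analysis to choose. Alpha, the 117 evaluable and 130 randomised per arm, the model, the data set and the result are the same whichever label is printed.

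The documents give no effect size or SD for CGI-S, so the gap between a Week 12 and a last-assessment result cannot be sized on that scale. It need not be, since only one of the two is planned. The conclusion rests on the visible text and on the assumption that the blacked-out passages do not redefine endpoint for CGI-S. Aligning the labels at a convenient revision would be good housekeeping, but nothing in the analysis depends on it.
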